6.4 Sample Size and Power

Sample Size Considerations: The primary hypothesis (**H1**) of this study is: 1) the CFA will detect changes in fat absorption with PERT administration in subjects with SBS. The sample size selected for the SBS cohort (n=26) is based upon our previous experience in cystic fibrosis (CF) and chronic pancreatitis (CP) in detecting changes over time before and after administration of PERT. Although few studies of fecal fat loss in subjects with SBS have been conducted, losses of about 48% of fat intake in the stool have been reported². For the CFA outcome, our experience has been in CF and pancreatic insufficiency (PI), with average CFA of 81±14% in one study³⁰ and 83±10% in another³¹ when subjects were on PERT. In comparison, healthy subjects have CFA ≥93%. From the literature for CP, a number of clinical trials have used CFA to describe fat malabsorption in subjects with CP and confirmed PI before and after administration of PERT. Ramesh et al³² found an increase in CFA from 66.7±14.0% before PERT to 88.9±5.2% after PERT (change of 22.7±12.2%) in adults with CP from India. Thorat et al³³, in a randomized controlled trial in India, saw CFA increase from 66.5±14.1 to 86.1±7.5% in those taking PERT compared to an increase from 67.0±14.0 to 72.9±11.5% for placebo, a treatment effect of 13.7% (95% CI: 9.1, 18.2) after 1 week of PERT. Drawing from the literature on CP in the absence of information for SBS, the change in CFA for subjects with CP and confirmed PI before and after PERT administration has ranged from 8 to 23% with the SD of that change ranging from 12 to 18%, but averaging at 14%. 22 subjects will have 80% power to detect a difference in means of 9% (increase in CFA% from 85 to 94% after PERT administration), assuming a SD of differences of 14%, using a paired t-test with $\alpha = 0.05$ two-sided significance level.

A secondary hypothesis (**H2**) in the study is: 2) the CNA and BC will detect changes in enteral protein absorption and stool energy losses, respectively, with PERT administration in subjects with SBS. There is limited data on CNA in SBS. One study² found that subjects with SBS had a CNA of about 47%. From the literature on CF, Trapnell et al⁵ reported an increase in CNA from $49.9 \pm 1.9\%$ to $85.1 \pm 1.9\%$ after administration of PERT. Borowitz et al⁴ reported a similar increase in both CFA and CNA following PERT, with CNA specifically increasing from as low as 57% to 74.6% following administration of PERT. Ramesh et al³² studied adults patients with CP and demonstrated that PERT resulted in a significant increase in CNA from $79 \pm 8.9\%$ to $85.5. \pm 3.8\%$ (change of $6.5 \pm 7.9\%$). Similar to CFA, for CNA, 22 subjects will have 80% power to detect a difference in means of 9% (increase in CNA% from 85 to 94% after PERT administration), assuming a SD of differences of 14%, using a paired t-test with $\alpha = 0.05$ two-sided significance level.

For the BC method, there is limited information for typical variability in calories lost in stool in either healthy subjects or those with malabsorption diagnoses. It has been reported that patients with SBS can have fecal energy losses as high as 1609 ± 561 kcal/day². Using 72-hour stool assessments, Wierdsma et al²⁸ has recently reported an average daily energy loss of 213 ± 66 kcal in 23 healthy adults. If we assume that approximately 200 kcal/day are lost in the stool of healthy subjects, 21 subjects in each group will have 80% power to detect a difference in means of 50 kcal (the difference in BC between a healthy group mean of 200 and a CP group mean of 250 kcal lost in stool) assuming that the common SD is 56 using a t-test with $\alpha = 0.05$. For BC, 22 subjects will have 80% power to detect a difference in means of 36 (decrease from 250 to 214 kcal/day in the stool), assuming a SD of differences of 56, using a paired t-test with $\alpha = 0.05$ two-sided significance level.

We expect no more than 20% attrition in this study given a relatively short time period between study visit #1 and study visit #2. By enrolling 26 subjects with SBS, we can account for attrition and also allow for the possibility of greater variability in the CFA, CNA, and BC outcomes within the SBS cohort for which we have had no previous experience.

Assessment of fat malabsorption using the MBT method (**H3**) will be conducted on a subset of 10 subjects and is exploratory. We have previous experience in CF and PI with detecting differences in the pharmacokinetic parameters C_{max} and AUC for HA and the HA/PA ratio⁷, and in detecting the percent change in HA absorption (from pharmacokinetic modeling) compared to healthy subjects⁹, and in detecting changes in subjects with CF before and after pancreatic enzyme administration^{7,9}. We have demonstrated differences in the magnitude of MBT outcomes (exposure metrics) indicating the degree of fat absorption in these subjects with varying treatment regimens of approximately 0.5 in both C_{max} and AUC HA/PA ratios with a standard deviation of ~ 0.7 . Differences of this magnitude were significant with samples of 16 subjects or less. Given the small sample size of this subset of subjects with SBS (n=10) and the known moderate variability within subjects in PA and HA with CF and PI^{7,9}, the use of the MBT method to detect fat malabsorption in SBS is considered an exploratory aim, and will inform future studies once effect sizes in the MBT outcomes are determined.

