3.3.2 Total Number of Study Sites/Total Number of Subjects Projected

The study will be conducted at two investigative site in the United States, the Children's Hospital of Philadelphia and the University of Pennsylvania. Recruitment will occur across regional centers as described above. All study visits will occur at The Children's Hospital of Philadelphia.

Recruitment will stop when 16 subjects with SBS between the ages of 4 and 17.9 years are enrolled and when 10 subjects with SBS between the ages of 18 years and 75 years are enrolled. It is expected that 26 subjects will be enrolled to produce at least 22 evaluable subjects.

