4.6 Subject Completion/Withdrawal

For subjects who were naïve to pancreatic enzyme medication at the start of the study, at the end of participation in the study (all collections are complete for Study Visit #2) Creon™ will be discontinued and they will resume their usual care without pancreatic enzyme medication. For subjects who were receiving pancreatic enzyme medication prior to the start of the study, at the end of participation in the study (all collections are complete for Study Visit #2), Creon™ will be discontinued and they will resume their usual care and will resume the pancreatic enzyme product and dose they were receiving before the study began.

Subjects may withdraw from the study at any time without prejudice to their care. They may also be discontinued from the study at the discretion of the Investigators for lack of adherence to study treatment or visit schedules, or adverse events. The Investigators or the Sponsor may also withdraw subjects who violate the study plan, or to protect the subject for reasons of safety or for administrative reasons. It will be documented whether or not each subject completes the clinical study. If the Investigator becomes aware of any serious, related adverse events after the subject completes or withdraws from the study, they will be recorded in the source documents and on the CRF. All subjects withdrawn from the study will receive a follow up phone call weekly for one month.

We expect investigator-based subject withdrawal to be rare. Subjects who experience an unexpected increase in ostomy or stool output during or following a baseline study will require additional monitoring of serum electrolytes and stools or ostomy output as needed. Those subjects who require changes to their parenteral nutrition for greater than three days or initiation of intravenous hydration and electrolyte repletion for greater than three days will not have a repeat MBT. These subjects will not require withdrawal from the study if both they and their primary care team for SBS agree to continued participation. Once electrolytes are stable, they will continue the study.

If a subject withdraws from the study for any cause, baseline data will be used for analysis.

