5.2 Efficacy

5.2.2. Diagnostic tests, Scales, Measures

Coefficient of fat absorption (CFA): The coefficient of fat absorption (CFA %) will be calculated based on a 72 hour stool and a 3-day weighed diet record collection performed after both Study Visit #1 and #2. Collection of stool will begin 24 hours after dietary records are started. All subjects will remain on their normal diet during stool collection. This includes the normal meals, snacks, and tube feeds that they typically receive. All subjects will receive a home collection kit and detailed instructions on stool collection. Stool collections will be performed at home and returned to CHOP upon completion. Subjects who are in diapers can either use plastic wrap to line the diaper or a urine collection bag secured around the anus for stool collection. They will then transfer stool from the plastic wrap or the collection bag to a stool collection container. All materials, including hand gloves, will be provided to ensure safe and accurate stool collection. All stool will be frozen until the time of analysis. Total fat content of the stool will be determined by a gravimetric method (Mayo Medical Laboratories, Rochester, MN). Total dietary intake of fat will be determined from the 3-day weighed food records. CFA % will be calculated based on determining the grams of fat consumed and the grams of fat excreted²⁷. CFA % will be compared for each subject before and after administration of pancreatic enzymes.

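### At the plan's own 20% attrition limit, 26 enrolled leaves 21 evaluable rather than at least 22, and no margin for the greater variability the 26 are also said to cover

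*Combined protocol and SAP*

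**What the plan says.** The protocol makes four linked statements about sample size.

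- Section 6.4 gives the power claim for the coefficient of fat absorption (CFA): "22 subjects will have 80% power to detect a difference in means of 9" percentage points, with an SD of differences of 14 and a paired t-test at two-sided 0.05. The claims for the coefficient of nitrogen absorption (CNA; 9 points, SD 14) and for bomb calorimetry (BC; 36 kcal/day, SD 56) also rest on 22 subjects.
- Section 6.4 sets the attrition limit: "We expect no more than 20% attrition in this study".
- Section 6.4 then gives the 26 two purposes: "By enrolling 26 subjects with SBS, we can account for attrition and also allow for the possibility of greater variability" in CFA, CNA and BC.
- Section 3.3.2 states the yield: "It is expected that 26 subjects will be enrolled to produce at least 22 evaluable subjects". It also fixes the enrolment total: "Recruitment will stop when 16 subjects with SBS between the ages of 4 and 17.9 years are enrolled" and 10 adults are enrolled.

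Section 6.4 describes the spread of CFA change in the chronic pancreatitis literature "with the SD of that change ranging from 12 to 18%, but averaging at 14" percentage points. Section 4.6 says of dropouts: "If a subject withdraws from the study for any cause, baseline data will be used for analysis". Section 6.5 announces an interim analysis to inform the number of subjects, without a rule.

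**The concern.** A stated minimum of evaluable subjects should hold at the attrition limit the plan sets for itself. Here 20% of 26 is more than the four subjects that separate 26 from 22, so the two sections appear to disagree.

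The four-subject difference is also spent twice: once on dropouts and once as protection against an SD larger than assumed. Section 6.4 takes its SD from chronic pancreatitis because the team has no earlier data in short bowel syndrome, so the second purpose matters. A reader of a null result, or someone deciding on sample size at the interim analysis, could believe the design has a tolerance for variability that it lacks when attrition reaches the limit.

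**Working it through.** **Inputs.** Enrolment 26, made up of 16 + 10 (3.3.2). Attrition limit 20% (6.4). Evaluable target 22 (3.3.2, 6.4). CFA difference 9, SD of differences 14, paired t-test, two-sided 0.05 (6.4). SD range 12 to 18 (6.4).

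**Method.** Power comes from the noncentral t distribution with n − 1 degrees of freedom and noncentrality (difference / SD) × √n.

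**Step 1: reproduce the plan's figure.** For n = 22, the noncentrality is (9/14) × √22 = 3.015 and the critical value is 2.080, giving power of 82.0%. The stated 80% is met. The smallest n that reaches 80% is 21: noncentrality (9/14) × √21 = 2.946, critical value 2.086, power 80.0%.

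**Step 2: evaluable number at the attrition limit.** 26 × 0.20 = 5.2, so at most five whole subjects can be lost within the limit.

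| Losses of 26 | Attrition | Evaluable |
|---|---|---|
| 4 | 15.4% | 22 |
| 5 | 19.2% | 21 |
| 6 | 23.1% (over the limit) | 20 |

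The statements in 3.3.2 and 6.4 agree for zero to four losses and conflict at five. Guaranteeing 22 at 20% attrition would take 22 / 0.80 = 27.5, that is 28 enrolled. The baseline data that section 4.6 retains for a withdrawn subject do not supply a pair, because CFA change is "based on a 72 hour stool and a 3-day weighed diet record collection performed after both Study Visit #1 and #2".

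**Step 3: how much extra variability the 26 can absorb.** Solve for the largest SD that keeps 80% power for a 9-point change.

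| Evaluable | Power at SD 14 | Largest SD for 80% power | Excess over 14 |
|---|---|---|---|
| 21 | 80.0% | 14.00 | 0.0% |
| 22 | 82.0% | 14.37 | 2.6% |
| 23 | 83.8% | 14.72 | 5.2% |
| 24 | 85.4% | 15.07 | 7.6% |
| 25 | 86.9% | 15.41 | 10.1% |
| 26 | 88.3% | 15.74 | 12.4% |

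The same percentages apply to CNA and BC, because the standardised effect is the same: 9/14 = 36/56 = 0.643. For BC the largest SD is 56.0 at 21 evaluable, 57.5 at 22 and 63.0 at 26.

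**Step 4: the top of the plan's own SD range.** An SD of 18 is 28.6% above 14 (18/14 = 1.286), beyond every row above.

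| Evaluable | Power for 9 points at SD 18 | Difference detectable with 80% power at SD 18 |
|---|---|---|
| 21 | 58.7% | 11.6 |
| 22 | 60.9% | 11.3 |
| 26 | 68.8% | 10.3 |

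These detectable differences lie within the 8 to 23 point range of change that section 6.4 cites. For the 13.7-point placebo-controlled effect quoted there, power at SD 18 is still about 91% with 21 evaluable and 96% with 26. The shortfall at SD 18 therefore concerns the 9-point target only.

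**The case against.** The attrition figure is a ceiling and the 22 is an expectation, so both can be true. They part company at a single value, five losses, and even there power at SD 14 is the stated 80%. The synopsis text also calls the enrolment numbers approximate. All of this is correct, and it is why the point is minor. It does not remove the mismatch: section 3.3.2 words the yield as a minimum, and the same section fixes the recruitment stop at 16 and 10.

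Section 6.4 promises no particular amount of extra variability and does not claim to cover an SD of 18. With zero to four losses there is some reserve, so the sentence is literally true in most of the plan's own scenarios. That also stands, and it argues for quantifying the sentence rather than deleting it. Pairing the highest cited SD with a target near the low end of the cited effects is a severe test, and it should be reported as such.

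The interim analysis in 6.5 may be the intended protection against unknown variability. It has no rule and no link to 6.4, and recruitment still stops at 26. It softens the concern but does not resolve it.

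Section 4.6 does not say that only baseline data are used for dropouts. Describing them at baseline is the natural reading, and nothing in the section says how a dropout would enter the paired comparison.

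**Conclusion.** The concern holds and is minor. At the plan's attrition limit, the evaluable number is 21 rather than at least 22, a difference of one subject and 2 points of power (80.0% against 82.0%). At that limit the 26 cover attrition but leave no allowance for an SD above 14. With fewer losses the allowance runs from 2.6% (22 evaluable) to 12.4% (all 26), and it never reaches the cited SD of 18.

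The planned test is unaffected, as is the claim of 80% power for 9 points at SD 14. The result assumes that attrition is the only source of loss and that a subject without both collections contributes no pair.

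**What to change.** In 3.3.2, state that 26 will be enrolled, that 20% attrition leaves about 21 evaluable if attrition is the only loss, and that 22 requires no more than four losses (15.4%).

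In 6.4, state that 21 evaluable subjects give 80% power for a 9-point change in CFA at an SD of differences of 14. Replace the general assurance about variability with figures: at 21 evaluable there is no allowance above SD 14; with all 26 evaluable, 80% power for 9 points holds up to an SD of about 15.7; at SD 18, power for 9 points is about 59% to 69% (21 to 26 evaluable), and the difference detectable with 80% power is about 11.6 to 10.3 points. Give the equivalent statement for CNA and BC, where the percentage allowance is the same.

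If the interim analysis in 6.5 is meant to deal with variability, say so in 6.4 and reconcile it with the recruitment stop in 3.3.2.

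The cost is rewording only. No subjects are added and the test does not change. The stated evaluable number falls from 22 to about 21, and the stated robustness becomes less favourable.

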6.5 Interim Analysis

An interim analysis is now planned to help inform decisions on the number of subjects needed to adequately power the study.

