
hormone concentrations at baseline and following administration of pancreatic enzymes both as evidence for proper digestion and as markers of intestinal adaptation.

SBS is a life threatening disease process with a paucity of noninvasive therapies that directly improve enteral absorption and improve patient outcome. If pancreatic enzyme medication is found to improve enteral absorption, this study will increase the clinical use of pancreatic enzymes in patients with SBS. This study will also provide further information on the mechanisms of malabsorption in patients with SBS, which could facilitate identification of other therapeutic targets to improve enteral absorption. It will provide the framework for larger studies to improve enteral absorption in patients with SBS.

Study Objective(s)	Primary: The primary objective of this study will be to determine if enteral absorption improves in subjects with SBS following therapy with pancreatic enzymes. Patients with SBS have significant fat malabsorption for several reasons ² . Lipid malabsorption in SBS occurs due to bowel resection, diluted pancreatic enzymes, altered enteroendocrine hormone signaling, acid hypersecretion, and rapid intestinal transit ⁶ . Pancreatic enzymes play a major role in enteral fat absorption. We propose that administering pancreatic enzymes to subjects with SBS will improve absorption of enteral nutrition. The primary hypothesis of this study is: H1: Pancreatic enzyme medication will improve enteral fat absorption in subjects with SBS, which will be indicated by an improved stool coefficient of fat absorption (CFA). Secondary: A secondary hypothesis of this study will aim to further characterize the effect that pancreatic enzyme medication will have on global nutrient absorption. H2: Coefficient of nitrogen absorption (CNA) and bomb calorimetry (BC) will detect changes in enteral protein absorption and stool energy losses, respectively, before and after therapy with pancreatic enzymes. We will address the unique difficulty of measuring enteral fat absorption in subjects with SBS. Fat absorption in a subset of subjects will be measured using the MBT. CCK concentration will also be measured in this subset as an additional area of exploration, as CCK plays a pivotal role in pancreatic enzyme secretion ⁶ . Additionally, we will explore the effect that improved nutrient absorption will have on intestinal adaptation by measuring changes in markers of intestinal mass and hormone levels.

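### The interim look in section 6.5 is meant to inform the sample size, but section 3.3.2 stops recruitment at 16 + 10 regardless, and 6.5 does not limit the look to the SD of the CFA change

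*Combined protocol and SAP*

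**What the plan says.** Section 6.5 (Interim Analysis) reads in full: "An interim analysis is now planned to help inform decisions on the number of subjects needed to adequately power the study". It gives no timing, no statistic to be examined, no decision rule, no minimum or maximum, and nothing about the final test.

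Section 3.3.2 sets the enrolment rule: "Recruitment will stop when 16 subjects with SBS between the ages of 4 and 17.9 years are enrolled", with a parallel limit of 10 adults. It adds: "It is expected that 26 subjects will be enrolled to produce at least 22 evaluable subjects". It does not refer to section 6.5. The Setting/Participants paragraph ahead of the Protocol Synopsis describes the same counts as approximate.

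Section 6.4 bases the size on the CFA: "22 subjects will have 80% power to detect a difference in means of 9" percentage points, with an SD of differences of 14, a paired t-test and two-sided alpha of 0.05. The SD is borrowed from chronic pancreatitis, "with the SD of that change ranging from 12 to 18%, but averaging at 14" per cent. The same section says "We expect no more than 20% attrition in this study" and cites "the possibility of greater variability in the CFA, CNA, and BC outcomes within the SBS cohort for which we have had no previous experience" as a further reason for enrolling 26.

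Section 6.3.1 (Efficacy Analysis) plans a paired t-test or Wilcoxon test without reference to an interim look. Sections 3.2 and 9.1 describe an open-label, non-randomised study in which every subject receives the enzyme.

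**The concern.** There are two problems.

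**The two rules do not connect.** A look meant to inform N is useful mainly when it shows that the planned N is too small. In that case 3.3.2 has recruitment stop at 26 enrolled whatever the look shows, so the study would either finish underpowered or need an amendment the plan does not foresee.

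**The look is not confined to the SD.** With one open-label arm, whoever holds the paired CFA differences can calculate the mean change as well as its SD. Section 6.5 does not exclude using the mean. If the mean drives N, the unadjusted 0.05 test rejects somewhat too often and the estimated change is biased upward. Using the SD alone avoids almost all of this.

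**Working it through.** **Inputs from the documents.** Target change 9 points; SD 14, range 12 to 18; 80% power; two-sided 0.05; 22 evaluable; attrition of at most 20% (all section 6.4). 26 enrolled as 16 + 10 (section 3.3.2).

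**1. Reproduce the plan's figure.** Power of a paired t-test is P(|T| > t(0.975, n-1)), where T is noncentral t with n-1 degrees of freedom and noncentrality (9/SD)·√n. For SD 14 and n = 22 the noncentrality is 0.643 × 4.690 = 3.015, and power is 82.0%. With n = 21 power is 80.0%. The stated 22 is sound.

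**2. The same formula across the plan's SD range.** Enrolment is evaluable N/0.8, rounded up.

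| SD | Evaluable for 80% power | Enrolled at 20% attrition | Power, 22 evaluable | Power, 26 evaluable |
|---|---|---|---|---|
| 12 | 16 | 20 | 91.8% | 95.7% |
| 14 | 21 | 27 | 82.0% | 88.3% |
| 16 | 27 | 34 | 71.1% | 78.7% |
| 18 | 34 | 43 | 60.9% | 68.8% |

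The 26 in section 3.3.2 is enrolled, so the last column requires no attrition at all. Even then, SD 16 and SD 18 miss 80%.

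**3. What an unrestricted look could do.** The documents give no rule, so these are assumptions: look at 13 completers; normal differences with SD 14; N reset to the smallest n with 80% power, between a minimum of 22 and a cap of 26, 34 or 52, all in evaluable subjects; final unadjusted two-sided 0.05 paired t-test. The simulation used 400,000 replicates (Monte Carlo standard error about 0.03 points near 5%).

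| What drives N | Type I error, cap 26 / 34 / 52 |
|---|---|
| Observed mean and SD, any large change shrinks N | 5.3 / 5.7 / 6.3% |
| Observed mean and SD, only a favourable change shrinks N | 5.1 / 5.3 / 5.6% |
| SD only, 9 points held | 5.1 / 5.2 / 5.2% |

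At a true 9-point change, the mean-driven rule biases the estimate by about +0.1 / +0.3 / +0.4 points, against a standard error of 14/√22 = 3.0. The SD-only rule gives no bias.

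**4. Why a minimum is needed.** If an SD-only look may also reduce N below 22, type I error is about 6% (look 13, cap 34: 6.0%). A chance low SD then both shortens the study and remains in the final test.

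**5. Attrition.** Getting 22 evaluable from 26 enrolled means a loss of 1 - 22/26 = 15.4%. At the full 20%, 26 × 0.8 = 20.8, or about 21. Power is 80.0% at 21 and 77.9% at 20.

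**The case against.** **The harm to the test is small.** This stands. H1 is directional ("Pancreatic enzyme medication will improve enteral fat absorption in subjects with SBS"), so the rule in which only favourable changes shrink N is the more relevant one. Against SD-only, the gap is then 0.05 points at cap 26 (5.12 against 5.07%) and 0.16 points at cap 34 (5.31 against 5.15%). The study calls itself exploratory. The conflict over recruitment is therefore the main issue.

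**The look only helps inform a decision, and the counts are approximate.** This partly stands: an amendment could enlarge the study. But a rounded description of 16 and 10 cannot stretch to 34 evaluable, and the operative sentence in 3.3.2 is a firm stop.

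**The effect size is uncertain too, and CNA and BC are also variable.** Both are true. Holding 9 points is a design choice: it fixes the change the study is sized to detect. CFA is the primary outcome, and section 6.4 sizes CNA and BC at the same ratio (9/14 = 36/56 = 0.643).

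**A reader might infer that 3.3.2 and 6.4 contradict each other on attrition.** They do not: 20% is a ceiling, and 15.4% lies within it. Nor would 28 enrolled guarantee 22 evaluable. If attrition really were 20%, the chance of reaching 22 is 38% with 26 enrolled and 68% with 28.

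**Conclusion.** The point holds, at moderate weight. Sections 6.5 and 3.3.2 cannot both be followed, short of an amendment, if the SD is 16 or more, which is inside the plan's own range. At SD 18, power is 61% with 22 evaluable and 69% with 26. This part rests only on the documents' figures.

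The second part, type I error of about 5.1-6.3% and bias of 0.1-0.4 points, rests on the assumed look, minimum and caps.

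A reader might go further and infer that an effect-driven look, or a stop for early success, is planned. Stopping on p < 0.05 at a look of 11 or 13 subjects, and otherwise continuing to 22, would give 8.1-8.5%. The documents do not support that reading: 6.5 names the number of subjects as its purpose and mentions no early claim. It permits an effect-driven look without stating one. It would also be wrong to say that every summary of the CFA change reveals the effect, since the SD of the differences does not show the mean.

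**What to change.** **Section 6.5.** State one re-estimation at a fixed number of completers, from the SD of the paired CFA differences only, with the 9-point target held. The mean change and p-value are neither reported at the look nor used. Evaluable N is never below 22 and never above a cap the sponsor sets in advance. The final test stays at two-sided 0.05.

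**Section 3.3.2.** Make recruitment stop at the N set under 6.5. Give the minimum and cap in evaluable subjects with the matching enrolment: at 20% attrition, 22, 26 and 34 evaluable need about 28, 33 and 43 enrolled. State how any change is divided between the two age groups. If the stop at 26 enrolled is to remain, say that the look can only prompt an amendment.

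**Minor.** Restate the expectation of at least 22 evaluable, because at the attrition ceiling 26 enrolled gives about 21. Little power is lost.

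**Cost.** Wording in two sections, and possibly more enrolment up to the cap. The look cannot support an early efficacy claim. It also recovers power only in part: with SD 18 and a look at 13, power rises from 61% with N fixed at 22 to 68% with a cap of 26 evaluable and 76% with a cap of 34, because an SD from 13 subjects is imprecise.
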